4.4. End of Study Definition

The end of the study is defined as the date that the last subject completes both the Week 12 Visit and Week 14 Safety Follow-up Telephone Call Visit, discontinues from the study, or is lost to follow-up.

A subject is considered to have completed the study if she completes 12 weeks of double-blind treatment at the Week 12 Visit.

5. Study Population

The study is being conducted in women with IBS-D or IBS-M, which is representative of the subject population to which the results will be generalized. Specific inclusion and exclusion criteria are specified below. Prospective approval of protocol deviations to recruitment and enrollment criteria, also known as protocol waivers or exemptions, is not permitted. Subjects may be rescreened **once** to meet inclusion criteria (see [Section 5.4](#)).

5.1. Inclusion Criteria

Subjects are eligible to be included in the study only if all of the following criteria apply at Visit 1 (Screening), unless otherwise noted:

1. Capable of giving written informed consent, which includes compliance with the requirements and restrictions listed in the informed consent form, including agreeing to patient registry verification.
2. Female, 18 to 70 years of age, inclusive
3. Body weight \geq 50 kg; body mass index < 45
4. Diagnosis of IBS-D or IBS-M according to the Rome IV criteria:
 - Recurrent abdominal pain, on average at least 1 day per week in the last 3 months, associated with 2 or more of the following criteria:
 - Related to defecation
 - Associated with a change in frequency of stool
 - Associated with a change in form (appearance) of stool
 - Diagnostic criteria must be fulfilled for the last 3 months, with symptom onset at least 6 months before diagnosis.
 - Subtyping performed by the predominant stool pattern present in a subject:
 - IBS-D: loose, mushy, or watery stools (Bristol Type 6 or 7) for $> 25\%$ of bowel movements and hard or lumpy stools (Bristol Type 1 or 2) for $< 25\%$ of bowel movements
 - IBS-M: hard or lumpy stools (Bristol Type 1 or 2) for $> 25\%$ of bowel movements and loose, mushy, or watery stools (Bristol Type 6 or 7) for $> 25\%$ of bowel movements
5. Has completed a colonoscopy according to the American Gastroenterological Association criteria (if necessary), with no clinically significant findings in the last 5 years
6. Willing and able, as assessed by the Investigator, to follow study instructions, including completing the subject diaries and quality of life questionnaires and attending all study visits
7. Willing and able to maintain regular diet for the duration of the study
8. Has no clinically significant findings on a physical examination or clinical laboratory tests that could interfere with study participation or confound study assessments, in the

opinion of the Investigator. Serum tissue transglutaminase antibody (IgA) must be negative. Fecal calprotectin testing is optional and should only be considered if there is a strong suspicion that the subject has IBD (eg, family history in a 1st degree relative, other genetic factors, etc.) or other organic disease, according to the clinical judgement of the investigator.

9. Women of childbearing potential must agree to use one of the contraception methods listed in [Section 10.6.1](#)
10. Agrees not to participate in another clinical trial while participating in this study
11. **At Baseline (Visit 3),**
 - Must continue to meet all inclusion criteria
 - During any 5 days in the 7 days immediately prior to Baseline (Visit 3), as reported in the subject's daily pain diary:
 - Subject must have a weekly average of “worst abdominal pain in the past 24 hours” score of ≥ 3.0 on a 0- to 10-point NRS (see [Section 10.9](#) for NRS)

5.2. Exclusion Criteria

Subjects are excluded from the study if any of the following criteria apply at Visit 1 (Screening), unless otherwise noted:

1. Diagnosis of IBS-C or IBS-U per Rome IV criteria
2. History of chronic idiopathic constipation or functional constipation
3. Current or history (in the past year) of substance or alcohol abuse, alcoholism, alcohol addiction, or drinks > 3 alcoholic beverages per day (one drink defined as 12 ounces of beer, 5 ounces of wine, or 1.5 ounces of distilled spirits)
4. History of clinically relevant liver disease or severe hepatic impairment (Child-Pugh Class C)
5. Pre-existing condition that has altered normal gastrointestinal anatomy (eg, prior bariatric surgery or gastric banding, solitary rectal ulcer syndrome)
6. History of or suspected mechanical gastrointestinal obstruction or current symptoms suggestive of gastrointestinal obstruction or infection
7. Diverticulitis within prior 3 months
8. Structural abnormality of the gastrointestinal tract or a disease or condition that can affect gastrointestinal motility
9. History of a gastrointestinal motility disorder other than IBS (eg, gastroparesis, intestinal pseudo-obstruction, achalasia, Parkinson's disease, multiple sclerosis, spinal cord injury)
10. Severe constipation or sequelae from constipation
11. Active duodenal or gastric ulcer
12. History of solitary rectal ulcer syndrome

13. Prior history of a gastrointestinal malignancy, inflammatory bowel disease, celiac disease
14. History of colitis (ischemic, lymphocytic, collagenous or radiation-induced) or hepatic and/or renal function that could interfere with the absorption, metabolism and/or excretion of the study drug (eg, carcinoid syndrome, amyloidosis)
15. Uncomplicated appendectomy within the past 3 months; subjects who had an appendectomy that was associated with any related complications or sequelae are eligible if the procedure was performed at least 6 months prior and all complications/sequelae have resolved
16. Planned gastrointestinal or abdominal surgery within the next 6 months
17. Co-existing gastroesophageal reflux disease or functional dyspepsia with symptoms predominant to IBS symptoms
18. Symptoms or diagnosis of a medical condition other than IBS that may contribute to abdominal pain (eg, interstitial cystitis; fibromyalgia currently being treated with pregabalin or gabapentin; and endometriosis with uncontrolled abdominal pain)
19. History of pancreatitis, structural diseases of the pancreas (including known or suspected pancreatic duct obstruction), known or suspected biliary duct obstruction, or sphincter of Oddi disease or dysfunction; acute, symptomatic cholecystitis or symptomatic cholelithiasis within the last 6 months is also exclusionary
20. Lactose intolerance not controlled by lactose-free diet
21. History or evidence of symptomatic arrhythmia, angina/ischemia, coronary artery bypass grafting surgery, percutaneous transluminal coronary angioplasty, cerebrovascular accident, transient ischemic attack, or any clinically significant cardiac disease
22. Clinically significant electrocardiogram (ECG) abnormality that, in the opinion of the Investigator, exposes the subject to risk by participating in the study.
23. Uncontrolled hypertension (sitting systolic blood pressure ≥ 180 mmHg and/or sitting diastolic blood pressure ≥ 100 mmHg) or resting heart rate (by pulse) > 100 beats per minute
24. Systolic blood pressure ≥ 160 mmHg but < 180 mmHg is excluded unless deemed by the Investigator as safe to proceed in this study and agreed to by the Sponsor's designated Medical Monitor; must be on stable hypertension medication for at least 3 months prior to entering Run-in (Visit 2)
25. Concurrent malignancy or history of any malignancy (within the last 5 years), except non-metastatic basal or squamous cell carcinoma of the skin that has been treated successfully
26. Uncontrolled diabetes mellitus defined by a hemoglobin A1C level $> 8\%$
27. Significant psychiatric or psychologic disorder that would preclude meaningful participation in the study (eg, bipolar disorders or schizophrenia; however, treated

depression on a stable regimen [eg SNRI, SSRI] is allowed) in the opinion of the Investigator

28. Presence of any unexplained alarm symptoms (eg, anemia, gastrointestinal bleeding, unintentional weight loss, suspected malignancy)
29. Use of any prohibited medications, such as eluxadoline, for which a subject cannot complete the appropriate washout period (see [Section 6.5.1](#)). Positive urine drug screen at Visit 1 is exclusionary except for the following situations:
 - Subjects who have a positive urine drug screen at Visit 1 due to a prohibited concomitant medication that can be washed out, the urine drug screen must be repeated at Visit 2 to determine if sufficient washout of the prohibited concomitant medication has occurred and to confirm eligibility
 - If the initial positive result at Visit 1 was due to a permitted concomitant medication (see [Section 6.5.2](#)), based on the clinical judgment of the investigator, a subject is still eligible and the urine drug screen would not need to be re-tested at Visit 2
30. Dose change for any medications requiring a stable dose (see [Section 6.5.2](#)) prior to the Screening Visit or plans to initiate or change the dosing of any of these medications during the study
31. Currently participating in or has participated in a study with an investigational compound or device or procedure within 28 days prior to screening
32. Currently participating in or has participated in a study with vibegron
33. ALT or AST > 2.0 times upper limit of normal (ULN), or bilirubin (total bilirubin) > 1.5 x ULN (or > 2.0 x ULN if secondary to Gilbert syndrome or pattern consistent with Gilbert syndrome)
34. Lipase > 2 x ULN
35. Estimated glomerular filtration rate < 30 mL/min/1.73 m²
36. Women who are pregnant, nursing, or planning a pregnancy during the study
37. History of sensitivity to any of the study drugs, or components thereof, or a history of drug or other allergy that, in the opinion of the Investigator, contraindicates study participation
38. At **Baseline (Visit 3)**, noncompliant with dosing during the 2-week Run-in Period (taking < 80% or > 120% of study medication)
39. Clinically significant medical or surgical history or any condition that could interfere with study participation or confound the assessments in the opinion of the study Investigator

5.3. Lifestyle Considerations

Subjects are expected to maintain their pre-study diet for the duration of the study. Alcoholic drinks must be limited to ≤ 3 per day (one drink is defined as 12 ounces of beer, 5 ounces of wine, or 1.5 ounces of distilled spirits).

5.4. Screen Failures

Screen failures are defined as subjects who consent to participate in the clinical study but are not subsequently randomized. A minimal set of screen failure information is required to ensure transparent reporting of screen failure subjects to meet the Consolidated Standards of Reporting Trials publishing requirements and to respond to queries from regulatory authorities. Minimal information includes demography, screen failure details, eligibility criteria, and any serious adverse event (SAE) that occurred within the Screening Period.

Individuals who do not meet the criteria for participation in the study (screen failures prior to initiation of run-in study medication) may be rescreened **once** upon consultation with, and approval by, the Sponsor's designated Medical Monitor, Sponsor, or its designee. Subjects who initiate Run-in study drug dosing may not be rescreened. Rescreened subjects will be assigned a new subject number, and both subject numbers will be linked to the subject, and a new informed consent with the new subject number should be signed. Screening assessments specified in [Section 1.3](#) should be repeated if subjects are rescreened.

6. Study Drug

6.1. Study Drugs Administered

Study Drug Name	Vibegron	Matched Placebo
Dosage Formulation	tablet	tablet
Identity of Formulation	75 mg	placebo
Route of Administration	oral	oral
Dosing Instructions	once daily	once daily
Packaging and Labeling	Study drug will be provided in HDPE bottles with child resistant caps. Each bottle will contain 32 tablets and will be labeled as required per country requirement.	Study drug will be provided in HDPE bottles with child resistant caps. Each bottle will contain 32 tablets and will be labeled as required per country requirement.
Manufacturer	Patheon, Cincinnati, Ohio, US	Patheon, Cincinnati, Ohio, US
Number and Timing of Drugs	Treatment Period: 1 tablet daily	Run-in Period: 1 tablet daily Treatment Period: 1 tablet daily

HDPE = high density polyethylene

The study drug will be supplied in bottles each containing 32 tablets (4-week supply) and labeled with the protocol number, bottle number, lot number, expiration date, study drug name (vibegron 75 mg or placebo tablets), number of tablets, directions for use, storage information, warning language (*Keep Out of Reach of Children. For Clinical Trial Use Only. To be used by qualified Investigators only. Caution: New Drug—Limited by United States Law to Investigational Use.*), and the US Sponsor name and address. Immediately before dispensing the study drug, the Investigator (or appropriately trained designee) will write the subject number, visit number, and the dispense date on the detachable panel of the label, which also includes the protocol number, bottle number and lot number.

6.1.1. Run-in Medications and Administration

During the single-blind Run-in Period, all subjects will take 1 tablet of study drug (ie, placebo) once daily for 2 weeks. All subjects will take their first dose of study drug at the study site as a witnessed dose. The date and time of the study drug dosing will be recorded. The Investigator will be aware that the study drug is placebo, but the subject will not know either the identity of the treatment or that entry into the double-blind Treatment Period is dependent on compliance with dosing in the Run-in Period. The matched placebo will be identical in appearance to the study drug administered during double-blind treatment.

6.1.2. Treatment Period Medications and Administration

During the double-blind Treatment Period, subjects will take 1 tablet of study drug (vibegron or matched placebo) once daily for up to 12 weeks. The appearance of the vibegron and placebo tablets will be identical. All subjects will take their first dose of study drug at the study site as a witnessed dose. The date and time of the study drug dosing will be recorded.

6.2. Preparation/Handling/Storage/Accountability

Clinical supplies must be stored in a secure, limited-access location under the storage conditions specified on the label.

Receipt and dispensing of study drug must be recorded by an authorized person at the study site.

Clinical supplies may not be used for any purpose other than that stated in the protocol.

The Investigator is responsible for keeping accurate records of the clinical supplies received from the Sponsor or designee, the amount dispensed to and returned by the subjects, and the amount remaining at the conclusion of the study. These records will be monitored throughout the study.

For all sites, the local country Sponsor personnel or designee will provide appropriate documentation that must be completed for drug accountability and return.

6.3. Measures to Minimize Bias: Randomization and Blinding

Single-blind (Run-in only) and double-blind (Treatment Period) techniques will be used. Vibegron and its matched placebo will be packaged identically so that the treatment blind is maintained. The subject, Investigator, and Sponsor personnel or delegate(s) who are involved in the treatment or clinical evaluation of the subjects will be unaware of the treatment group assignments during the double-blind Treatment Period. Subjects will be centrally assigned to randomized study drug using an interactive web response system (IWRS) and the randomization schedule generated by the Sponsor or designee. Before the screening is initiated at each site, login information and directions for the IWRS will be provided.

The IWRS will be programmed with blind-breaking instructions. In case of an emergency, the Investigator has the sole responsibility for determining if unblinding of a subject's study drug assignment is warranted. Subject safety must always be the first consideration in making such a determination. If the Investigator decides that unblinding is warranted, the Investigator should make every effort to contact the Sponsor or designee prior to unblinding a subject's study drug assignment unless this could delay emergency treatment of the subject. If a subject's study drug assignment is unblinded, the Sponsor or designee must be notified within 24 hours after breaking the blind. The date and reason that the blind was broken must be recorded in the source documentation.

At the end of the study, the official, final database will be frozen and unblinded after medical/scientific review has been performed, and data have been declared final and complete. The Sponsor will be granted access to the unblinded database in order to analyze the data. A clinical study report will be prepared after all subjects complete the study.

6.4. Study Drug Compliance

Study drug compliance will be closely monitored by counting the number of tablets dispensed and returned. Before dispensing new study drug at applicable visits, study site personnel will make every effort to collect all unused study drug and empty bottles.

The study site will keep an accurate drug disposition record that specifies the amount of study drug administered to each subject and the date of administration.

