Visit Window		± 4 days		± 4 days	± 4 days	± 4 days	± 4 days	-7 days	Safety Follow-up call will occur 7 to 14 days after the last dose of study drug (includes window of -7 days) ^a
Laboratory assessments (chemistry, hematology, urine dipstick) ^b	X		X	X	X	X	X		Tests specified in Section 10.2
Serum tissue transglutaminase antibody (IgA)	X								Screening only
12-lead ECG	X								Screening only; supine
Dispense/collect subject diary		X Dispense					X Collect		Bowel Movement Diary will record bowel movement frequency and form, bowel urgency, and recurrent bowel movements; Pain Diary will record worst abdominal pain and use of rescue meds
Dispense Run-in study drug		X							Daily dosing
Administer witnessed dose of study drug		X	X						
Randomization			X						

	Screening	Run-in	Double-blind Treatment					Safety Follow-up	Notes
	Visit 1	Visit 2	Visit 3	Visit 4	Visit 5	Visit 6	Visit 7	Telephone Call	
Day/Week	Day -42 to -15	Day -14	Baseline Day 1	Week 2 (Day 15)	Week 4 (Day 29)	Week 8 (Day 57)	Week 12 or Early WD (Day 85)	Week 14 or 14 days after last dose (at the latest)	
Visit Window		± 4 days		± 4 days	± 4 days	± 4 days	± 4 days	-7 days	Safety Follow-up call will occur 7 to 14 days after the last dose of study drug (includes window of -7 days) ^a
Dispense new bottle of double-blind study drug for daily dosing			X		X	X			At Visit 4 (Week 2), the Visit 3 (Baseline) bottle will be checked for compliance and returned to subject
GIS			X	X	X	X	X		Before vital signs and blood draw
WPAI			X			X	X		Before vital signs and blood draw
IBS-QoL			X			X	X		Before vital signs and blood draw
Additional questions on abdominal pain (see Section 10.8.4)			X	X	X	X	X		Before vital signs and blood draw

AE = adverse event; avg = average; ECG = electrocardiogram; GIS = Global Improvement Scale; IBS = irritable bowel syndrome; IBS-QoL = irritable bowel syndrome quality of life; IWRS = interactive web response system; min = minutes; SAE = serious adverse events; WD = withdrawal; WPAI = Work Productivity and Activity Impairment

^a Safety Follow-up telephone call will occur only for randomized subjects who complete Week 12 or withdraw from the study early.

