10.7.3. Baseline, Visit 3 (Day 1)

- Assess inclusion/exclusion criteria
- Review concomitant medications
- Administer questionnaires (GIS, WPAI, IBS-QoL, and additional abdominal pain questions)
- Record blood pressure (average of 3 results; record each reading in the source document), body temperature, pulse, and weight
- Perform brief physical examination (heart, lungs, abdomen, external genitalia, perianal area, and any other areas as needed)
- Perform urine pregnancy test; if positive, perform serum test (subject may not begin double-blind treatment if serum pregnancy test is positive)
- Perform laboratory assessments, including urine dipstick
- Obtain subject randomization assignment
- Dispense double-blind study drug
- Administer witnessed dose of study drug
- Review AEs/SAEs

10.7.4. Double-blind Treatment Period Week 2 (\pm 4 days), Visit 4

- Administer questionnaires (GIS and additional abdominal pain questions)
- Review AEs/SAEs
- Review concomitant medications, including use of rescue medication from diary
- Record blood pressure (average of 3 results; record each reading in the source document), body temperature, and pulse
- Perform laboratory assessments, including urine dipstick
- Review remaining double-blind study drug from Baseline (Visit 3) for compliance and return to subject

10.7.5. Double-blind Treatment Period Week 4 (\pm 4 days), Visit 5

- Administer questionnaire (GIS and additional abdominal pain questions)
- Review AEs/SAEs
- Review concomitant medications, including use of rescue medication from diary
- Record blood pressure (average of 3 results; record each reading in the source document), body temperature, and pulse
- Perform laboratory assessments, including urine dipstick
- Dispense double-blind study drug

10.7.6. Double-blind Treatment Period Week 8 (\pm 4 days), Visit 6

- Administer questionnaires (GIS, WPAI, and IBS-QoL, and additional abdominal pain questions)
- Review AEs/SAEs
- Review concomitant medications, including use of rescue medication from diary
- Record blood pressure (average of 3 results; record each reading in the source document), body temperature, and pulse
- Perform laboratory assessments, including urine dipstick
- Dispense double-blind study drug

10.7.7. Double-blind Treatment Period Week 12 (\pm 4 days [Visit 7]), or Early Withdrawal

- Administer questionnaires (GIS, WPAI, IBS-QoL, and additional abdominal pain questions)
- Collect subject diary
- Review AEs/SAEs

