10.8. Appendix 8: Patient-Reported Outcomes Questionnaires

10.8.1. Global Improvement Scale

Global improvement assessment asks subjects to evaluate their current IBS status by asking the following question: How would you rate your IBS signs or symptoms overall over the past 7 days?

- 1) significantly relieved
- 2) moderately relieved
- 3) slightly relieved
- 4) unchanged
- 5) slightly worse
- 6) moderately worse
- 7) significantly worse

A responder is defined as a subject who answered that their symptoms were either moderately relieved or significantly relieved [Gordon, 2003; Lembo, 2001].

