7.1. Extent of Exposure

The duration of exposure during the double-blind treatment period will be expressed as the time in days from the first dose as recorded on the Study Drug Administration CRF page at Visit 3 through to last treatment day (inclusive) as recorded on the End of Treatment CRF

page, excluding any days where it is recorded that an interruptions has occurred on the AE CRF page and as indicated on the COVID19 CRF page.

Interruption in days = date started – date stopped + 1

This is given by the following formula:

Duration (days) = date last double blind dose – date first double blind dose – interruption days + 1

Duration of exposure will be summarized by treatment group for the SAF using summary statistics for continuous variables. The proportion of subjects with Dose Interruptions ≥ 2 weeks (14 consecutive days) will be summarized by treatment group, if applicable.

A listing will present the treatment start and end date together with the date of interruption, and the overall days of exposure.

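### Collecting leftover tablets at Visits 5 and 6 conflicts with the 32-tablet bottle and the ±4-day windows: a compliant woman can be without study drug for up to 4 days before Visit 6

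*Protocol*

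**What the plan says.** - **Bottle size.** Protocol Section 6.1: "The study drug will be supplied in bottles each containing 32 tablets (4-week supply". Section 6.1.2 has one tablet taken daily, for no more than 12 weeks.
- **Dispensing.** The row "Dispense new bottle of double-blind study drug for daily dosing" in the Schedule of Assessments (Section 1.3) is marked at Visits 3, 5 and 6 only. It refers to a single bottle each time.
- **Leftovers.** Under Section 6.4, before new drug is dispensed, "study site personnel will make every effort to collect all unused study drug and empty bottles". Handing a bottle back is described for one visit only: "At Visit 4 (Week 2), the Visit 3 (Baseline) bottle will be checked for compliance and returned to subject".
- **Visit days.** Section 1.3 sets Visits 5, 6 and 7 at Days 29, 57 and 85, each ±4 days. The windows are anchored to Day 1, not to the previous visit. No maximum interval between visits and no resupply between visits is given.
- **What is measured then.** The GIS is completed at Visits 3 to 7 and asks: "How would you rate your IBS signs or symptoms overall over the past 7 days". SAP Section 4.2.4.2 defines diary Week 9 as Days 57-63.
- **Exposure.** SAP Section 7.1 counts days from first to last dose, "excluding any days where it is recorded that an interruptions has occurred on the AE CRF page" or on the COVID-19 page. SAP Section 7.2 uses the same interruption days when it sets the expected number of tablets.

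**The concern.** Each rule is reasonable alone, but together they do not fit. The four spare tablets per bottle would cover a 4-day delay if each window ran from the previous visit. They do not cover an early visit followed by a late one when both windows are fixed to Day 1. Because the spare tablets are taken back at the early visit, a woman who does everything asked of her can run out.

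At stake are untreated days that the plan itself creates in the vibegron arm. Women on placebo miss tablets too but lose no active drug, so any effect in the affected week is diluted. The Visit 6 questionnaires, blood pressure and laboratory tests would then follow several drug-free days. The SAP would also record those days as exposure and as missed doses, because a stock-out is neither an AE interruption nor, ordinarily, a COVID-19 entry.

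**Working it through.** **Inputs.** 32 tablets per bottle (Section 6.1); one tablet daily (6.1.2); one bottle at each of Visits 3, 5 and 6 (1.3); leftovers collected before dispensing (6.4); Visit 5 on Days 25-33, Visit 6 on Days 53-61, Visit 7 on Days 81-89 (1.3).

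**The plan's own figure.** Four weeks × 1 tablet = 28 doses, so 32 tablets cover a nominal interval with 32 − 28 = 4 spare. This agrees with the label of a 4-week supply.

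**Longest permitted intervals.** If the visit-day dose comes from the new bottle, a bottle issued on day *s* covers days *s* to *s* + 31, and gap days = max(0, interval − 32).

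| Interval | Longest | Tablets | Largest gap | Days without tablets |
|---|---|---|---|---|
| Visit 3 to 5 | 33 − 1 = 32 | 32 | 0 | none |
| Visit 5 to 6 | 61 − 25 = 36 | 32 | 4 | 57-60 |
| Visit 6 to 7 | 89 − 53 = 36 | 32 | 4 | 85-88, if dosing continues that long |

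If the Visit 5 dose comes from the old bottle, the new one lasts from Day 26 to Day 57 and the largest Visit 5-to-6 gap is 3 days (Days 58-60).

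**How often, Visit 5 to 6.** A gap needs the deviation at Visit 6 minus that at Visit 5 to be at least 5 days. Of the 9 × 9 = 81 pairs of in-window days, 9 − *k* have difference *k*, so the count is 4 + 3 + 2 + 1 = 10. The documents give no distribution of visit days; the figures below assume independent deviations.

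- Uniform over ±4 days: 10/81 = 12.3%, with a mean gap of 2 days when one occurs.
- Normal-shaped weights on the whole days −4 to +4, with SD 1.5, 2 or 2.5: about 1.5%, 4.2% or 6.5%, with a mean gap of 1.3 to 1.6 days.

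Averaged over all women this is about 0.25 days (uniform) or 0.02 to 0.11 days (clustered), at most 0.25/84 = 0.3% of 12 weeks.

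**Where the days fall.** Every Visit 5-to-6 gap day lies in Days 57-60, so at most 4 of the 7 days of diary Week 9 are untreated and no other diary week is touched. The primary endpoint (SAP 4.3.1.1) requires response in at least 6 of 12 weeks. For a Visit 6 on Day 61, the same 4 days are in the 7-day GIS recall.

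**Total supply.** 3 × 32 = 96 tablets. If leftovers stayed with the woman, 64 tablets would last to Day 64 (latest Visit 6: Day 61) and 96 to Day 96 (latest Visit 7: Day 89). No in-window schedule then has a gap. The shortfall therefore comes from the collection rule, not from the amount of drug.

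**Effect on compliance.** Over Days 1-84, a 4-day gap with no other missed dose gives 80/84 = 95.2%. For the SAP 3.2.1 criterion of under 80% in Weeks 8-12, the ceiling is 31/35 = 88.6% if the period is Days 50-84, or 24/28 = 85.7% if it is Days 57-84.

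**The case against.** **The collection rule is softer than it looks.** Section 6.4 speaks of effort. The visit lists for Visits 5 and 6 (10.7.5, 10.7.6) show dispensing but no collection, which is listed only for Visit 7 (10.7.7). If sites leave tablets with the women, the gap disappears. This stands in part. But Section 6.4 ties collection to the visits at which new drug is dispensed, and after Visit 3 those are Visits 5 and 6. A site that follows it creates the gap, and one that does not departs from the protocol.

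**It is a worst case with little effect on the endpoint.** This stands. An early visit must be followed by a late one, at most one of 12 weeks is touched, and the average loss is a fraction of a day.

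**A reader might infer that the secondary endpoint, GIS at Week 12, is compromised in the same way.** The documents do not establish this. Section 6.1.2 limits dosing to 12 weeks, and 32 tablets issued on Day 53 last exactly to Day 84. On that reading Days 85-88 follow the end of the course, whatever the bottle size. They are a supply gap only if dosing runs to the Week 12 Visit, as the completion definition in Section 4.4 may imply. The SAP window for the Week 12 GIS extends to 14 days after the last dose, so the plan already accepts a GIS completed off drug.

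**A reader might also infer that stock-outs push compliant women out of the per-protocol set.** The ceilings above stay over 80%. Further missed tablets would be needed: two on the Days 57-84 reading (22/28 = 78.6%) and four on the Days 50-84 reading (27/35 = 77.1%). The SAP list of deviations is also only indicative, with membership settled before unblinding.

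**Conclusion.** The inconsistency between Visits 5 and 6 holds. Following the stated rules exactly, a fully compliant woman can be without tablets for up to 4 days (3 if the Visit 5 dose comes from the old bottle), all within Days 57-60.

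The share affected rests on an assumed distribution of visit days: 12.3% if uniform, about 1.5% to 6.5% if clustered with SD 1.5 to 2.5 days. The expected effect on the primary endpoint is small, and no dilution of the treatment difference has been estimated. The exposure and compliance derivations in SAP 7.1 and 7.2 would misclassify the gap days.

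For Visits 6 to 7 the point is conditional. Sections 4.4 and 6.1.2 leave open whether dosing ends at 12 weeks or at the Week 12 Visit, and only the second reading makes Days 85-88 a supply gap before the Week 12 GIS. No woman can have both gaps: the first needs Visit 6 on Day 58 or later, the second on Day 56 or earlier.

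**What to change.** 1. Reconcile Protocol Sections 1.3, 6.1, 6.4 and 10.7.5-10.7.7 so that the collection rule, bottle count and visit windows agree, and the tablets on hand cover the longest permitted interval between dispensing visits. The 96 tablets already supplied are enough if leftovers are not withdrawn, as already happens at Visit 4.
2. Reconcile Sections 4.4 and 6.1.2 by stating whether dosing ends at 12 weeks or at the Week 12 Visit. This review takes no position on which.
3. Add one sentence to SAP 7.1 and 7.2: days with no tablets on hand are a supply interruption, counted neither as exposure nor as non-compliance. They can be identified from dispensing dates and tablet counts.

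The cost is a wording change and one SAP sentence, with no added visits or drug. If leftovers stay with the women, tablet counts per bottle become slightly harder to reconcile.
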